9. STUDY ASSESSMENTS

9.1 Medical History

A complete medical history, including concomitant medications, will be obtained to assess study eligibility. All clinically-significant medical conditions, surgeries, and procedures should be recorded. If the subject is not normally seen at the study center, it may be necessary to obtain medical records to confirm study eligibility. For details, refer to the Study Reference Manual.

9.2 Demographics

Demographic data on each subject (e.g., age, gender, race, ethnicity) will be obtained at the Screening visit.

9.3 Concomitant Medications

Current concomitant medications will be recorded. For details, refer to the Study Reference Manual.

9.4 Physical Examination

Physical examinations will be conducted on each subject at the specified visit and will include at minimum: general appearance, head, eyes, ears, nose, and throat (HEENT); as well as cardiovascular, dermatologic, respiratory, gastrointestinal, musculoskeletal, and neurologic systems. For details, refer to the Study Reference Manual and the Physical Exam Guidelines.

9.5 Vital Signs

Vital signs, including height, weight, systolic/diastolic blood pressure, heart rate, respiratory rate, and temperature will be recorded. For details, refer to the Study Reference Manual.

9.6 Joint Range of Motion (JROM)

Since MPS II subjects are known to suffer from joint stiffness and skeletal deformities, a series of JROM assessments will be conducted, as permitted by the subject's capacity. For details refer to the Study Reference Manual and the Physical Exam Guidelines.

9.7 Neurological Cranial Nerve Exam and Muscle Strength Testing of Upper Extremities

Mutations in SMCHD1, a gene identified as a low-level off target of SB-913, have been associated with FSHD type 2. No detectable modification to SMCHD1 in muscle or nerve cells by SB-913 is expected at the doses used in this study. Nevertheless, for safety evaluation of SB-913, facial and upper body muscle strength will be tested, as permitted by the subject's capacity. For details, refer to the Study Reference Manual and the Physical Exam Guidelines.

9.8 Electrocardiogram (ECG)

12-lead ECGs will be obtained to monitor cardiac function/conduction. For details, refer to the Study Reference Manual.

9.9 Echocardiogram (ECHO)

Standard 2-dimensional Doppler ECHOs will be obtained to evaluate cardiac function. The measurements will include chamber volumes, ventricular wall thickness, left ventricular ejection fraction, regional wall motion, and valvular morphology and function. For details, refer to the Study Reference Manual and the Imaging Guidelines.

9.10 Chest X-Ray

Chest X-Rays (also known as AP radiograph of the chest) will be obtained to evaluate the general health and study eligibility of the subject per the Principal Investigator's clinical judgement. For details, refer to the Imaging Guidelines.

9.11 Pregnancy Testing and Contraception Requirements

Pregnancy testing will be conducted on all female subjects of childbearing potential (for details, refer to the Laboratory Manual).

A female subject is considered of childbearing potential (i.e. fertile) following menarche and until becoming post-menopausal unless permanently sterile. A postmenopausal state is defined as no menses for 12 months without an alternative medical cause. Permanent sterilization methods include hysterectomy, bilateral salpingectomy, and bilateral oophorectomy.

Female subjects of childbearing potential with a positive pregnancy test at Screening will not be enrolled in the study.

Female subjects of childbearing potential will have a serum pregnancy test at the Screening and Baseline visits. Urine pregnancy test will be performed on the Day 0 visit if >7 days from Baseline pregnancy test. Subsequently, urine pregnancy tests will be done at the indicated visits (see Section 6 and Appendix 1) until at least 3 consecutive plasma samples after administration of SB-913 are negative for AAV2/6. Additional pregnancy tests will be performed at any visit at which pregnancy status is in question. A serum pregnancy test will be performed in the event of a positive or equivocal urine pregnancy test result, or can be performed if pregnancy test by urine is not feasible at the discretion of the Principal Investigator.

Pregnancy in a subject or a subject's partner must be reported to the Sponsor (see Section 10.7).

Both male and female sexually mature subjects must agree to use a barrier contraceptive method for prevention of AAV transfer as follows: for female subjects this means that the subjects' partners must use a condom from dosing with SB-913 and until at least 3 consecutive plasma samples after administration of SB-913 are negative for AAV2/6; for male subjects this means that the subjects must use a condom and must refrain from sperm donation from the time of SB-913 are negative for AAV2/6; for AAV2/6.

Additionally, female participants of child-bearing potential who have not undergone a total hysterectomy or bilateral salpingo-oophorectomy and are sexually active must consent to use a highly effective method of contraception as listed below from dosing with SB-913 and until at least 3 consecutive plasma samples after administration of SB-913 are negative for AAV2/6. Examples of highly effective methods of contraception include:

- Combined (estrogen and progestogen containing) hormonal contraception associated with inhibition of ovulation (e.g., oral, intravaginal, transdermal).
- Progestogen-only hormonal contraception associated with inhibition of ovulation (e.g., oral, injectable, implantable).
- Intrauterine device or intrauterine hormone-releasing system.
- Bilateral tubal occlusion.

- Male partner sterilization, also called vasectomy.
- Sexual abstinence (i.e., refraining from heterosexual intercourse during the entire period of risk associated with SB-913, when this is in line with the preferred and usual lifestyle of the subject).

For details, refer to the Laboratory Manual.

9.12 Clinical Laboratory Tests

Clinical laboratory tests are summarized in Table 2. For details, refer to the Laboratory Manual.

Hematology	Urine (with microscopic examination)	Serum Chemistry
Complete blood count with	Glucose	Sodium (Na)
differential and platelet	Protein	Potassium (K)
count	Bilirubin	Chloride (Cl)
	Blood	Carbonate $(CO_3^{2^-})$
	pH	Calcium (Ca)
	Specific gravity	Phosphate (PO_4^{3-})
		Blood urea nitrogen
		Creatinine
		Glucose
		Uric acid
		Lactate dehydrogenase (LDH)

Table 2.Clinical Laboratory Tests.

For pediatric cohorts, assessments requiring blood draws should be obtained over multiple days if needed to ensure that no greater than 0.8 mL/kg of blood is drawn in any 24-hour period.

9.13 Liver Panel

Liver function testing will include assessment of AST, ALT, total and direct bilirubin, alkaline phosphatase, LDH, albumin, and total protein levels. Since liver function testing is important to closely monitor for transaminitis due to AAV-mediated immunogenicity in this study, it is strongly recommended that subjects refrain from consuming alcohol and from taking liver-toxic medications and herbal supplements for the study period of one year after SB-913 administration. Liver panel will be performed twice a week for at least the first 20 weeks post-SB-913 infusion and may be conducted at home if the subject is remote. Blood samples for liver panel shall be drawn 2-4 days apart when possible, except for the first week when they will be drawn on the Day 1 and Day 7 visits. Subsequent to discontinuation of prednisone or equivalent corticosteroid, liver panel will be performed at all study visits for the duration of the study. Liver panel does not need to be drawn as a separate blood sample if Clinical Laboratory Tests are obtained at the same visit. For details, refer to the Laboratory Manual.

9.14 MPS II Gene Sequencing

MPS II gene sequencing will be performed at Screening to confirm the clinical diagnosis of MPS II. The assay may be performed on blood or saliva samples; however for pediatric subjects (cohorts 5 through 8), saliva samples are strongly preferred. For details, refer to the Laboratory Manual.

9.15 Single-Nucleotide Polymorphism (SNP) Analysis

A SNP assay will be performed at Screening to identify polymorphisms in the ZFN-targeted region of the albumin locus. The assay may be performed on blood or saliva samples; however for pediatric subjects (cohorts 5 through 8), saliva samples are strongly preferred. Subjects with polymorphisms in the ZFN-targeted region of the albumin locus are not eligible to participate in this study. For details, refer to the Laboratory Manual.

9.16 Viral Load

Testing for HIV, HBV, and HCV will be conducted at Screening. Subjects with a diagnosis of HIV or evidence of active HBV or HCV infection are not eligible to participate in this study. For details, refer to the Laboratory Manual.

9.17 Neutralizing Antibodies to AAV2/6

The level of neutralizing antibodies to AAV2/6 will be measured at Screening to assess the subject's pre-existing immune response to AAV2/6. Subjects with elevated pre-existing neutralizing antibodies to AAV2/6 are not eligible to participate in this study. For details, refer to the Laboratory Manual.

9.18 GAG Testing in Urine and Blood

GAGs are metabolites that accumulate in MPS II due to lack of active IDS enzyme. GAG accumulation is responsible for diffuse organ toxicity and damage in MPS II. To monitor the effect of SB-913 administration, GAG levels (including total GAG, DS GAG, and HS GAG) will be measured in urine and tissues (including blood, liver tissue, and CSF) throughout this study. Samples GAG testing in blood and urine must be obtained 7 days after ERT administration (+/1 day) and prior to the next ERT infusion. GAG and IDS levels in blood will both be measured concurrently from the same blood sample. For details, refer to the Laboratory Manual.

9.19 Circulating AFP Level

Clinical laboratory measurement of AFP will be performed to monitor for potential development of malignancy. Subjects with elevated abnormal circulating AFP at Screening are not eligible to participate in this study. For details, refer to the Laboratory Manual.

9.20 Vector Genome PCR

Plasma, saliva, urine, stool, and semen (males only) samples will be analyzed by PCR to determine clearance of SB-913 vector genomes. Each type of sample (plasma, saliva, urine, stool, semen) should be collected until 3 consecutive specimens of that sample type are reported as negative or undetectable for vector genome. Collection of semen samples may be waived for pediatric subjects (cohorts 5 through 8) at the discretion of the Principal Investigator. For details, refer to the Laboratory Manual.

9.21 Pulmonary Function Tests (PFTs)

MPS II is often associated with significant pulmonary complications. PFTs are a common method for evaluating respiratory function, and will be conducted in this study as permitted by the subject's capacity. For details, refer to the Study Reference Manual.

9.22 6-Minute Walk Test (6MWT)

A 6MWT will be performed, as permitted by subject's capacity, to measure endurance following the American Thoracic Society Guidelines. For details, refer to the Study Reference Manual.

9.23 Neurocognitive Abilities Tests

WASI-II, WPPSI-IV, and BSID-III are widely-used neurocognitive tests that have been validated and are easily administered. Given the broad age-range of study participants and variability of CNS involvement due to MPS II, the appropriate test will be determined for each subject at Screening visit following a neurocognitive abilities assessment. Based on this initial evaluation, either the WASI-II, WPPSI-IV, or the BSID-III will be administered to each subject beginning at the Baseline visit. The same test should be used throughout the duration study when possible to allow for longitudinal evaluation.

The VABS-II test is given to all subjects and provides a measure of adaptive behaviors, including ability to cope with environmental changes, to learn new skills, and to demonstrate independence.

The tests will be administered by a trained psychologist or psychometrist to determine neurocognitive function over time after SB-913 administration. Neurocognitive testing will be conducted as permitted by the subject's capacity. For details, refer to the Study Reference Manual.

9.24 MRI of Liver

MRI of the liver is commonly used to evaluate liver pathology in patients with MPS II, and will be performed in this study to evaluate liver and spleen volumes, as well as to screen and monitor for the potential development of liver masses. For details, refer to the Study Reference Manual and the Imaging Guidelines.

9.25 MRI of Brain and Cervical Spine

MRI of the brain and cervical spine is commonly used to evaluate neurological and skeletal complications in patients with MPS II, and will be performed in this study to evaluate for changes in clinical soft tissue and/or bone appearance. The baseline MRI of brain and cervical spine may be obtained at Screening (together with MRI for liver) instead of at Baseline at the Principal Investigator's discretion. For details, refer to the Study Reference Manual and the Imaging Guidelines.

9.26 Adrenocorticotropic Hormone Stimulation (Cosyntropin) Test

An ACTH stimulation test will be performed prior to beginning and discontinuing a prednisone or equivalent corticosteroid regimen to evaluate adrenocortical function. During the test, vital signs should be monitored and recorded every hour. For details, refer to the Study Reference Manual.

9.27 IDS Testing in Blood

IDS activity in blood will be measured to determine whether IDS is being produced and is active. IDS activity measurements may be conducted on plasma, serum, whole blood, dried blood spot, leukocytes, or other blood component. Samples must be obtained 7 days after ERT administration (+/- 1 day) and prior to the next ERT infusion. IDS and GAG testing in blood will both be measured concurrently from the same blood sample. For details, refer to the Laboratory Manual.

9.28 Liver Biopsy

The proposed mechanism of action of SB-913 is to introduce the hIDS transgene into a precise location in the albumin locus. To determine the efficiency of SB-913, liver tissue will be obtained by liver biopsy, unless contraindicated by the Principal Investigator or physician, and analyzed by histopathologic examination, testing for GAG levels, and high-throughput sequencing of the albumin locus. Further, subjects with an elevated AFP or MRI mass suspicious for HCC or greater than 2 cm will undergo liver biopsy. Histopathologic examination and genomic analysis will be performed to determine the origin and nature of the tumor. For details, see Appendix 4 and refer to the Study Reference Manual.

9.29 Lumbar Puncture

MPS II often causes neurocognitive decline due to a buildup of GAGs in the brain. To determine if GAG levels in the CSF are changed after SB-913 administration, lumbar punctures will be performed on all subjects, unless contraindicated by Principal Investigator or physician. CSF samples may also be tested for cell count, total protein, glucose, and other MPS-related biomarkers. For details, refer to the Study Reference Manual.

9.30 Immunogenicity Assays

Exploratory research assays, including total antibodies to AAV2/6, ZFN, and IDS immunogenicity will be performed. At the discretion of the Principal Investigator, this assessment may be waived for pediatric subjects (cohorts 5 through 8) to reduce required blood volumes. For details, refer to the Laboratory Manual.

9.31 Laboratory Assessments in Pediatric Subjects

Although safety monitoring of subjects with clinical laboratory testing is necessary in this study, the potential impact of taking multiple blood samples in children must be assessed at all times. Therefore, all blood draws in pediatric cohorts should be minimized when possible to ensure the safety and welfare of the subjects, particularly in the case of younger children. In accordance with accepted guidance, no more than 1% of total blood volume (0.8 mL/kg) should be drawn in pediatric subjects in any 24-hour period unless medically-indicated based on the judgement of the Principal Investigator (Veal et al, 2014). In addition, it is encouraged to utilize procedures to minimize any pain and distress associated with blood sampling when possible, such as use of intravenous catheters, collection from central catheters if in place, use of local anesthesia for needle sticks, etc. (For details, refer to the Laboratory Manual).

9.32 ERT Administration Log

Frequency of ERT administration will be studied before and after administration of SB-913. Therefore, each dose of ERT given to the subject from the time of Screening will be recorded on the ERT Administration Log, including date and time of start and stop of ERT infusion. At each indicated visit, documentation of all ERT administration since the last visit must be obtained and confirmed. An assumed standing schedule (e.g., weekly) should not be used.

9.33 ERT Clinical Assessment

A clinical assessment of the need for ERT must be conducted at the ERT Withdrawal Follow-Up visit. The Principal Investigator should determine if chronic weekly ERT infusions will be resumed or if the subject may continue without ERT, and indicate the decision on the appropriate eCRF. The assessment will be made based on the clinical judgement of the Principal Investigator and in

consultation with the Medical Monitor, taking into account all information available (which may include but is not limited to AEs, clinical laboratory testing, IDS levels, GAG levels, 6MWT, PFTs, and other available data). The ERT Clinical Assessment may be completed again at any time post-ERT withdrawal if there is a clinically significant change in the status of the subject's ERT administration.

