11.4 ERT Withdrawal

ERT using Elaprase (idursulfase) or equivalent is the only approved therapy for MPS II. ERT is beneficial but has significant drawbacks, which include the need for continuous life-long treatment; development of neutralizing antibodies; lack of efficacy in the brain (due to inability to cross the blood-brain barrier); continued cardiac, musculoskeletal, and upper airway complications; and the inconvenience and cost of weekly IV infusions (Tomanin et al, 2014).

The goal of SB-913 treatment is to abrogate or decrease the need for enzyme replacement therapy, by using engineered zinc finger nucleases (ZFNs) to site-specifically integrate a corrective copy of the enzyme iduronate-2-sulfatase (hIDS) transgene into the genome of the subject's own hepatocytes in vivo, resulting in life-long, liver-specific expression of IDS. Therefore, subjects who have received SB-913 may no longer require weekly administration of ERT, and may be considered for withdrawal of ERT (if applicable).

ERT withdrawal will be a controlled process with additional safety monitoring to reduce potential risk to the subject, and is an optional part of the study.

ERT withdrawal may be initiated by the Principal Investigator after consultation with the Sponsor, and only in subjects who are willing and who meet all of the following criteria:

- Are ≥ 12 weeks post-administration of SB-913.
- Are medically stable and can tolerate temporary discontinuation of ERT in the judgement of the Principal Investigator.
- Agree to additional safety monitoring and lab testing until ERT Withdrawal Follow-Up visit (see Appendix 2).

Study visits associated with ERT withdrawal may occur concurrently or independent of regular scheduled study visits, but should be combined with regular scheduled study visits whenever possible to reduce study burden. When combined, assessments associated with ERT withdrawal that are duplicated at the regular scheduled study visits should be waived (see Appendix 1). The ERT Withdrawal Follow-Up visit can occur at any time up to 12 weeks after ERT withdrawal at the discretion of the Principal Investigator.

ERT does not need to be restarted after the ERT Withdrawal Follow-Up visit. However, ERT may be re-initiated at any time based on clinical circumstances or at the judgement of the Principal Investigator.

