ERT withdrawal may be repeated if previously unsuccessful. However, ERT withdrawal may not be attempted until at least 12 weeks after ERT has been resumed, and only at the discretion of the Principal Investigator and in consultation with the Sponsor. Subjects undergoing repeat ERT withdrawal must be willing and meet the criteria for initial ERT withdrawal listed above.

Documentation of dosing and administration of all ERT should be obtained and recorded on the ERT Administration Log.

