# 2.2.2 Secondary Endpoints

The following are secondary endpoints for this study:

- Change from Baseline in:
  - o IDS activity measured in blood.
  - o Total GAG, DS GAG, and HS GAG levels (expressed as ratio to creatinine) measured in urine.
- Monthly and annualized frequency and dose of idursulfase (or equivalent ERT).
- AAV2/6 clearance measured by vector genomes in plasma, saliva, urine, stool, and semen by PCR.

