#### 6.2 Secondary Endpoints and Analyses

Secondary endpoints will be summarized by presenting descriptive statistics of actual values and changes from baseline at each visit, where applicable. The secondary endpoints consist of the changes from baseline over time in the following assessments:

- IDS activity measured in plasma
- Assessments will be conducted at Screening, Baseline, Weeks 2, 4, 6, 8, 12, 16, 20, 24, 36, 48, Months 15, 18, 21, 24, 27, 30, 33, 36/End of Study (EOS), and at any Early Termination Visit. Total GAG, dermatan sulfate (DS) GAG, and heparin sulfate (HS) GAG levels measured in urine

At each sampling time point, the actual value and the change from baseline for IDS activity and urine GAG levels will be summarized using descriptive statistics and plotted over time by treatment cohort.

For subjects who undergo ERT withdrawal, changes from pre- to post- ERT withdrawal in the frequency and dose of ERT infusions will be evaluated and summarized using monthly, quarterly, and annualized total dose and number of infusions. Duration of ERT withdrawal may also be analyzed. The ERT withdrawal period is defined as the date recorded on the ERT Withdrawal Trigger CRF form to the first date after ERT withdrawal recorded on the ERT administration.

• AAV2/6 clearance measured by vector genomes in plasma, saliva, urine, stool, and semen by PCR

AAV2/6 clearance measured by vector genomes in the different samples will be plotted over time by treatment cohort.

CONFIDENTIAL Page 15 of 28

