# 10.2 Appendix B: ERT Withdrawal Schedule of Events

PROCEDURE*	ERT Withdrawal Visit (a)	ERT V	Vithd	trawal 1 +/-	ERT Withdrawal Follow- Up Visit (within 12 weeks of ERT withdrawal) (c)					
		1	2	3	4	6	8	10	12	
Concomitant Medications	X	X	X	X	X	X	X	X	X	X
Physical Examination	X									X
Vital Signs (d)	X									X
AE Assessment	X	X	X	X	X	X	X	X	X	X
ERT Administration Log	X	X	X	X	X	X	X	X	X	X
Clinical Laboratory Tests	X									X
Liver Panel (e)	X	X	X	X	X	X	X	X	X	X
GAG Testing in Urine	X	X	X	X	X	X	X	X	X	X
IDS / GAG Testing in Blood	X	X (g)	X	X (g)	X	X	X	X	X	X
PFTs (f)	X									X
6MWT (f)	X									X
ERT Clinical Assessment										X

\* Assessments associated with ERT withdrawal that are duplicated at regular scheduled study visits should be waived if visits are combined (see Appendix 1).

- a) ERT Withdrawal visit may occur at or at any time after the Week 12 visit (refer to Section 11.4 for additional guidance).
- b) ERT Withdrawal Monitoring visits will take place on a weekly basis for the first 4 weeks, and on a biweekly basis for the last 8 weeks following the ERT Withdrawal visit until the ERT Withdrawal Follow-Up visit. ERT Withdrawal Monitoring visits have assessments that do not require evaluation at the clinical site, and may therefore be conducted at home if the subject is remote. Blood and urine samples at these visits may be collected by a qualified home health nurse. Assessments for AEs and concomitant medications may be conducted by study staff over the phone.
- c) The ERT Withdrawal Follow-Up visit can occur at any time up to 12 weeks after ERT withdrawal at the discretion of the Principal Investigator. ERT does not need to be restarted at the end of the ERT Withdrawal Follow-Up visit.
- d) Vital signs (weight, systolic/diastolic blood pressure, heart rate, respiratory rate, and temperature; refer to the Study Reference Manual).
- e) Liver panel does not need to be drawn as a separate sample if Clinical Laboratory Tests are obtained at the same visit.
- f) As permitted by subject's capacity.
- g) May be waived for pediatric subjects (cohorts 5 through 8) at the discretion of the Principal Investigator to minimize required blood volumes.

CONFIDENTIAL Page 27 of 28

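### The SAP does not summarise the recorded decision on continued need for ERT, and its pre/post infusion counts include the ERT-free interruption that withdrawal itself creates

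*Protocol*

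**What the plan says.** Protocol 11.4 gives the aim: "The goal of SB-913 treatment is to abrogate or decrease the need for enzyme replacement therapy". Withdrawal is optional. The investigator starts it after consulting the sponsor, at least 12 weeks after dosing, in willing and medically stable subjects. The Follow-Up visit may fall at any point up to 12 weeks after withdrawal, and ERT may be restarted at any time. Section 11.4 also foresees failure: "ERT withdrawal may be repeated if previously unsuccessful", provided at least 12 weeks have passed since ERT was resumed.

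Protocol 9.33 makes an assessment of need mandatory: "A clinical assessment of the need for ERT must be conducted at the ERT Withdrawal Follow-Up visit". The investigator has to settle this question: "if chronic weekly ERT infusions will be resumed or if the subject may continue without ERT, and indicate the decision on the appropriate eCRF". Section 9.33 allows a further assessment later if the subject's ERT status changes materially.

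In the SAP, the "ERT Clinical Assessment" appears only as a row in the Appendix B schedule. The planned analysis is in SAP 6.2: for subjects who withdraw, "changes from pre- to post- ERT withdrawal in the frequency and dose of ERT infusions will be evaluated and summarized". Totals are to be given per month, per quarter and per year. SAP 6.2 adds: "Duration of ERT withdrawal may also be analyzed". It defines the withdrawal period as running from the date on the withdrawal trigger form to the first later ERT date. Protocol 13.5 describes the same count-based summary and does not use the 9.33 decision either.

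**The concern.** The trial aims to change the need for ERT and collects a yes/no judgement on exactly that. The plan summarises infusion counts instead, and withdrawal lowers those counts whatever the subject's need. While ERT is stopped, a subject with no benefit and a subject with full benefit look the same.

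The SAP does not say where the pre and post windows start and end, what counts as a successful or failed withdrawal, or how a second attempt is handled. The withdrawal period also has no end rule for a subject who never resumes, which is the outcome the trial hopes for.

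At stake is how the ERT secondary endpoint is read. A subject who went back to weekly ERT can be reported as having reduced use, and a repeated failure can add to that reduction. With 2 to about 4 subjects per cohort (SAP 9), one such subject can dominate a cohort's summary.

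**Working it through.** The documents give no ERT-reduction figure to reproduce, so the check is a simple count.

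**Inputs**
- Schedule before withdrawal: weekly, 52 per year. This is an assumption; Protocol 11.4 speaks of weekly administration.
- Time off ERT, L: up to 12 weeks to the Follow-Up visit (Protocol 11.4).
- Gap before a repeat attempt: at least 12 weeks after resumption (Protocol 11.4).
- Longest post window: 36 months of follow-up (Protocol 3.4), about 156 weeks, less 12 weeks before the earliest withdrawal = 144 weeks.
- Post window, W: not defined in the SAP. Assumed to start at the withdrawal date.
- True change in need: none. The subject resumes weekly ERT.

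**Formula.** Infusions in the post window = W − L. Annualized rate = 52 × (W − L)/W. Change = −L/W.

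| Weeks off | Window (weeks) | Infusions without withdrawal → with failed withdrawal | Annualized rate | Change |
|---|---|---|---|---|
| 12 | 12 | 12 → 0 | 0 | −100% |
| 12 | 13 | 13 → 1 | 4.0 | −92% |
| 12 | 26 | 26 → 14 | 28.0 | −46% |
| 12 | 52 | 52 → 40 | 40.0 | −23% |
| 12 | 144 | 144 → 132 | 47.7 | −8% |
| 8 | 52 | 52 → 44 | 44.0 | −15% |
| 4 | 52 | 52 → 48 | 48.0 | −8% |
| 4 | 144 | 144 → 140 | 50.6 | −3% |
| 12 + 12, with 12 on between | 52 | 52 → 28 | 28.0 | −46% |
| 12 + 12, with 12 on between | 144 | 144 → 120 | 43.3 | −17% |

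A subject who never resumes shows 0 infusions and −100% in every window. Over the first 12 weeks, a 12-week failure is therefore identical to a success.

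**Sensitivity to the windows**
- Post window starting at resumption: 52 before, 52 after, change 0%. A subject who never resumes then has no post window at all.
- Pre window limited to the 12 weeks after dosing, with 1 to 2 infusions omitted around dosing (Protocol 3.5 omits ERT in the infusion week; the count of 1 to 2 is an assumption). The pre rate is 52 × 11/12 = 47.7 or 52 × 10/12 = 43.3. Against 40.0 over 52 weeks the change is −16% or −8%. Against 47.7 over 144 weeks it is 0% or +10%.

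**Effect of the proposed reporting.** The failed 12-week subject is counted under ERT resumed. The interruption shows 0 infusions in 12 weeks. The time after it shows 52 per year against 52 before, a change of 0%. A subject who stays off is counted under continued without ERT and shows 0 per year afterwards. The two are now distinguishable.

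**The case against.** The strongest reply is that the endpoint is ERT use, not need. The secondary objective is the frequency of ERT administration (Protocol 2.2, SAP 2.1.2), and fewer infusions is a true description of use. The 9.33 decision is an open-label clinical judgement without fixed criteria and is not a listed endpoint. That stands: leaving the decision out does not make the stated endpoint wrong, and ERT-free time should not be dropped from it. Dropping it could also leave little post time for a subject who moves to the long-term follow-up study soon after the Follow-Up visit.

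Second, failures need not stay hidden. Later monthly or quarterly counts would return to about four per month, duration of withdrawal may be analysed, and SAP 4 promises subject listings by cohort. This also stands in part. However, the duration analysis is optional and has no end rule for subjects who never resume, and a listing is not a summary. Nothing links any of these to the recorded decision.

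Third, a reader might infer that the protocol imposes the interruption, so that the result is wholly fixed by design. Protocol 11.4 does not support that: withdrawal is voluntary, the Follow-Up date is flexible and ERT may restart at any time. A subject doing badly can have a short interruption and a small artefact.

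Finally, the study is descriptive, and no formal decision in the documents depends on this summary.

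**Conclusion.** The point holds in a limited form. The one direct record of continued need for ERT has no planned summary. The planned pre/post counts include time off ERT that withdrawal itself creates, under windows and rules that the SAP leaves undefined. With weekly ERT, no benefit, full ERT beforehand and a post window from the withdrawal date, a failed 12-week withdrawal appears as −92% (13 weeks), −23% (52 weeks) or −8% (144 weeks). Two failed 12-week attempts appear as −46% (52 weeks) or −17% (144 weeks).

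A reader might go further and conclude that every withdrawer will look favourable whatever window is used, or that the plan makes failures impossible to detect. The documents support neither. Some windows give 0% or up to +10%, and the monthly and quarterly counts or the listings may show ERT returning. What is missing is a planned summary that separates failed from successful withdrawals. The change should be made, because following the plan as written can report reduced ERT use for a subject who returned to weekly infusions.

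**What to change.** Amend SAP 6.2 in two ways.

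1. Add a table by cohort with the number of subjects withdrawn from ERT, the 9.33 decision at Follow-Up (resumed or continued without ERT), any later change of that decision, the number still off ERT at last contact, and the number of attempts.
2. Keep the overall pre/post summary of ERT use, but define its pre and post windows, how repeat attempts enter it, and how the withdrawal period ends for a subject who never resumes. Alongside it, report infusion number and dose separately for the interruption (withdrawal date to the Follow-Up visit or first resumed infusion, whichever comes first) and for the time after it. State the follow-up time available in each.

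No clinical procedure changes and no new data are needed: the decision is on the eCRF and every infusion is in the ERT Administration Log (Protocol 9.32). The cost is SAP wording and one small extra table. The reported reduction in ERT use may look less favourable, and the time after the interruption may be short for some subjects.
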